## VARIABLES

The sociodemographic and clinical variables to be collected are: age, marital status, employment status, language, family situation, clinical history of interest, personal and family history of psychopathology, pharmacological, psychological and substance use treatment, tumor type, stage and medical treatment.

The psychological variables will be assessed by means of the following questionnaires: Big-5 brief personality questionnaire, HADS anxiety and depression questionnaire, COPE-28 coping questionnaire, brief illness perception questionnaire, MOS-SSS social support questionnaire, SF-12 quality of life questionnaire, resilience scale, ERQ emotional regulation scale and the program satisfaction questionnaire.

The biological variables to be determined are:

- In blood: levels of cytokines related to tumor development and inflammation (IL1 $\beta$ , IL-2, IL-6, IL-8, IL-10, IFN- $\gamma$  and TNF- $\alpha$ ); monoaminergic activity (tyrosine, phenylalanine, tryptophan, quinurenine, serotonin, quinurenic acid and 3HK) and IDO activity (through the tyrosine-kinurenine ratio).
- In saliva: the diurnal cortisol cycle and estrogen and testosterone levels.

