## **STUDY PROTOCOL. Elkar laguntza**

### AIMS

The general aim of the present research will be to evaluate the effectiveness of a peer social support intervention in cancer patients at the Onkologikoa Foundation of Guipuzcoa. Specifically, the immediate and long-term effect that such intervention will have on symptoms of psychological distress, quality of life, coping strategy, perception of social support, perception of the disease and emotional regulation will be evaluated. As a secondary aim of this study, we intend to evaluate the immediate and long-term effect of the peer social support intervention on the immune system (through the determination of the levels of cytokines IL-1 $\beta$ , IL-2, IL-6, IL-8, IL-10, IFN- $\gamma$  and TNF- $\alpha$ ), on the monoaminergic system (through the determination of plasma levels of serotonin, tyrosine, phenylalanine, tryptophan, quinurenine, quinurenic acid and 3-HK), on the HPA axis (through the measurement of the diurnal cycle of cortisol), and on sex hormones (through the measurement of estradiol and testosterone levels), systems that have been related both to the development of anxious-depressive symptoms and to the development, progression and recurrence of cancer.

In addition, it will be studied at what time the application of the program is most effective, being applied in newly diagnosed patients (experimental group 1) and in patients who have just finished medical treatment (experimental group 2).

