For each GE1 patient, a specific volunteer will be selected based on the patient's tumor type and medical treatment, although depending on the availability of volunteers, other variables will also be taken into account: age, preferred language, time availability, partner, children and socioeconomic level. Once selected, each patient and volunteer will be given a letter of introduction to the other, in order to learn basic information about the patient before the first session. The social peer support program will begin the week prior to the start of medical treatment. There will be a total of eight sessions, one every fifteen days approximately, for a total duration of four months. The duration of each session will be as follows: the first and second sessions will last approximately one hour, the following sessions will last an average of 30 minutes. Patients and volunteers will be given the possibility to request a change of person in case they feel that the bond between them is not adequate.

Once the support program has been completed in EG1, a second evaluation of clinical, psychological and biological variables will be carried out, and, in addition, satisfaction with the intervention program will be evaluated, thanks to the Treatment Satisfaction Questionnaire. In GE2, the evaluation of clinical, psychological and biological variables will be carried out four months after the first evaluation. A third evaluation of all participants will be carried out 15 days after receiving the news of the end of the medical treatment (chemotherapy or radiotherapy). At four months and eight months after the end of medical treatment (chemotherapy or radiotherapy), the fourth and fifth evaluations will be carried out. In each of these evaluations the procedure will be as follows: each participant will be given a questionnaire of psychological measures to fill in before their appointment and four saliva collection tubes, which they will have to collect the day before their appointment. In addition, they will be scheduled for a blood draw and for the collection of the questionnaires and saliva samples.

GE2 patients will participate in the peer support program, but the application of this intervention will take place 15 days after receiving the news of the end of medical treatment. The intervention in this group will have the same characteristics and the same evaluations as those of GE1.

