#### DATA ANALYSIS

The relationships between the variables collected will be analyzed with the SPSS version 22.0 statistical package and with the JMP 10 statistical package. In all the analyses performed, the following variables will be controlled: type and duration of medical treatment and pharmacological treatment. Repeated measures analyses will be performed to study the effect of the intrasubject support program. Also, in order to study the possible physiological and psychological differences between experimental groups 1 and 2, analysis of variance (ANOVA) will be carried out. Pearson's correlation coefficient will be used to analyze the relationships between the different physiological and psychological variables considered in this study. Several General Linear Models (GLM) analyses will be performed to determine the predictive value of each of the variables in the possible benefit obtained after the application of the program. To study the interactions in each of the GLM analyses performed, a simple regression analysis will be carried out.

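### IDO activity is defined by a tyrosine-kynurenine ratio that omits tryptophan, the substrate of IDO; probably a wording slip, but nothing else in the plan corrects it

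*Combined protocol and SAP*

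**What the plan says.** The blood bullet in VARIABLES gives the cytokines, then "monoaminergic activity (tyrosine, phenylalanine, tryptophan, quinurenine, serotonin, quinurenic acid and 3HK"), and then "IDO activity (through the tyrosine-kinurenine ratio"). Neither a formula nor a numerator and denominator is given.

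AIMS places the biological measures under the secondary aim and names the same seven analytes: "plasma levels of serotonin, tyrosine, phenylalanine, tryptophan, quinurenine, quinurenic acid and 3-HK". It mentions neither IDO nor any ratio.

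DATA ANALYSIS does not name IDO either, but its methods are stated for physiological variables in general. For the groups: "possible physiological and psychological differences between experimental groups 1 and 2, analysis of variance (ANOVA) will be carried out". For associations: "Pearson's correlation coefficient will be used to analyze the relationships between the different physiological and psychological variables considered in this study".

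On the later evaluations, METHODS says of participants: "they will be scheduled for a blood draw and for the collection of the questionnaires and saliva samples". The first evaluation also includes a blood draw.

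**The concern.** IDO (indoleamine 2,3-dioxygenase) starts the conversion of tryptophan towards kynurenine. An index of its activity built from blood levels therefore compares kynurenine with tryptophan. The plan's ratio leaves tryptophan out and brings in tyrosine, which is not on that pathway.

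Anyone who follows the text literally will have a tyrosine value to hand, so nothing in the data would flag the mistake. A variable labelled IDO activity could then enter the group comparisons and correlations while partly reflecting tyrosine. It could suggest a change in IDO when kynurenine/tryptophan has not moved, or hide one when it has.

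**Working it through.** **Is the definition corrected or explained anywhere?** Three readings could rescue the text.

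- *Tyrosine used as another word for tryptophan.* No. Both appear as separate analytes in the VARIABLES bullet and again in AIMS.
- *A formula given elsewhere.* No. AIMS lists analytes only, METHODS describes sampling, and DATA ANALYSIS names model types.
- *A slip in drafting or translation.* Plausible. The same bullet spells the metabolite both 'quinurenine' and 'kinurenine', and tryptophan, which the index needs, is on the assay list. This explains the error but does not remove it.

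**How many values are involved?** METHODS gives 120 patients and five evaluations, so 120 × 5 = 600 values at most, before any attrition.

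**How do the two indices differ?** The plan has no figure to reproduce here, and it gives no analyte means, SDs or correlations. The changes below are assumptions, set at 10%, 20% and 30%. Because the plan does not state an orientation, the written ratio is shown both ways. Kyn, Trp and Tyr are kynurenine, tryptophan and tyrosine.

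| Assumed change (10 / 20 / 30%) | Kyn/Trp | Tyr/Kyn | Kyn/Tyr |
|---|---|---|---|
| 1. Tyr up alone | 0 / 0 / 0% | +10.0 / +20.0 / +30.0% | -9.1 / -16.7 / -23.1% |
| 2. Kyn up, Trp down | +22.2 / +50.0 / +85.7% | -9.1 / -16.7 / -23.1% | +10.0 / +20.0 / +30.0% |
| 3. As 2, with Tyr also up | +22.2 / +50.0 / +85.7% | 0 / 0 / 0% | 0 / 0 / 0% |
| 4. Kyn up alone (20% only) | +20% | -16.7% | +20% |

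Arithmetic:

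- Row 1: Tyr/Kyn is multiplied by 1.1, 1.2, 1.3. Kyn/Tyr is multiplied by 1/1.1 = 0.909, 1/1.2 = 0.833, 1/1.3 = 0.769.
- Row 2: Kyn/Trp is multiplied by 1.1/0.9 = 1.222, 1.2/0.8 = 1.500, 1.3/0.7 = 1.857. Kyn/Tyr is multiplied by 1.1, 1.2, 1.3, and Tyr/Kyn by the reciprocals.
- Row 3: Kyn/Trp as in row 2. The written ratio is multiplied by 1.1/1.1 = 1.2/1.2 = 1.3/1.3 = 1.
- Row 4: Kyn/Trp and Kyn/Tyr are multiplied by 1.2, and Tyr/Kyn by 1/1.2 = 0.833.

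In row 2 the share of the Kyn/Trp change that the written ratio shows, on the log scale, is

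- ln 1.1 / ln(1.1/0.9) = 47%
- ln 1.2 / ln 1.5 = 45%
- ln 1.3 / ln(1.3/0.7) = 42%

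These shares are the same in either orientation, because a reciprocal changes only the sign of the logarithm.

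Row 1 is a false signal, row 2 an attenuated one and row 3 a masked one. In row 4 nothing is lost except that the sign depends on orientation.

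**The case against.** The other side accepts that the phrase is wrong if read literally and disputes its weight.

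- *It is an editorial slip, not a considered analytic choice.* Probably so, and it is treated that way here. It is nevertheless the only definition of a listed study variable, so it needs correcting.
- *Almost nothing depends on it.* Largely right. AIMS and DATA ANALYSIS do not name IDO, and no sample size or decision rule uses it. Its route into reported results is inferred from analyses described for physiological variables in general. Because tryptophan and kynurenine are assayed anyway, the intended ratio can be recomputed at any time. This keeps the point at the lowest level of importance.
- *The scenarios are constructed.* True. The zero in row 3 holds because tyrosine and kynurenine are assumed to rise by the same percentage, and the 42 to 47% shares follow from assuming equal and opposite changes. They show how the two indices can part company and do not estimate what will happen in this trial. Likewise, 600 is a ceiling with no attrition.
- *Asking for kynurenine as numerator is convention.* Partly right: on the log scale the reciprocal carries the same information. But the plan states no log transformation, and on the raw scale the means in an ANOVA and a Pearson coefficient differ between a ratio and its reciprocal. One orientation should be fixed in advance; which one matters less.

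**Conclusion.** The point holds as a minor one. The written definition of IDO activity omits the enzyme's substrate, includes an amino acid from another pathway, and is corrected nowhere in the document.

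It touches one derived variable under the secondary aim. It matters only if the text is followed literally and the index is then carried into the general analyses.

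The conclusion that the definition is wrong rests on the meaning of the enzyme's name, since the document neither expands IDO nor names its substrate. It does not depend on the assumed analyte changes. With no SDs or correlations available, nothing can be said about how closely the two indices would agree in these patients. That the wording is a slip is a probable reading, which only the sponsor can confirm.

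**What to change.** The sponsor should confirm that tryptophan was intended and replace the parenthesis in VARIABLES with: *IDO activity (kynurenine/tryptophan ratio, kynurenine as numerator)*, computed from the levels already determined in the blood samples. The spelling of kynurenine can be made uniform in the same edit.

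The cost is one line of text, with no new assay, sample or visit. Making the change before analysis also avoids having to explain a redefined variable later.

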#### DATA ANALYSIS

The relationships between the variables collected will be analyzed with the SPSS version 22.0 statistical package and with the JMP 10 statistical package. In all the analyses performed, the following variables will be controlled: type and duration of medical treatment and pharmacological treatment. Repeated measures analyses will be performed to study the effect of the intrasubject support program. Also, in order to study the possible physiological and psychological differences between experimental groups 1 and 2, analysis of variance (ANOVA) will be carried out. Pearson's correlation coefficient will be used to analyze the relationships between the different physiological and psychological variables considered in this study. Several General Linear Models (GLM) analyses will be performed to determine the predictive value of each of the variables in the possible benefit obtained after the application of the program. To study the interactions in each of the GLM analyses performed, a simple regression analysis will be carried out.

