Each of the volunteers will have to be with 2 or 3 patients at the same time since some authors state that performing support to more than one patient can compensate for a poor relationship with another patient, as well as serve as support in the event of a patient's death (Moulton et al., 2013). The volunteer-patient sessions will be conducted in rooms set up for this purpose in the Carlos Santamaría building of the UPV/EHU. After each session with the patients, each volunteer will have to attend an individual session with the program coordinator [name] to discuss their emotions and reactions after performing the intervention. Psychological supervision of the volunteers is a fundamental part of avoiding retraumatization and the possible appearance of anxious-depressive symptoms (Giese-Davis et al., 2006). Likewise, volunteers will have to participate in group sessions every two months with the rest of the volunteers and the program coordinator [name] in order to strengthen group cohesion, resolve doubts, detect needs and carry out the necessary training.

The patients in this study will be 120 patients with various types of cancer from the Onkologikoa Foundation. Each patient will be matched with a volunteer depending on the type of tumor and medical treatment, since some authors state that for the support program to be effective, the volunteers must have had the same type of tumor and medical treatment as the patients (Pistrang et al., 2012). This is why it will be necessary to homogenize the group of volunteers as much as possible so that the sample of patients has as little variability as possible. The inclusion criteria are: having received the diagnosis of cancer in the last month; not having started medical treatment; the tumor type and medical treatment coinciding with any of the volunteers. The exclusion criteria are: relapse; suffering or having suffered from a serious mental disorder (according to DSM-V criteria). The recruitment of these patients will take place just after the diagnosis, and the professionals of the Onkologikoa Foundation will be in charge of offering this type of intervention to the patients who meet the inclusion criteria of the study.

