Those patients who are interested in participating will be informed about the present research project by the coordinator of the program and by the members of the research team of the Onkologikoa Foundation and it will be these same people who will be in charge of giving the information sheet and the informed consent, and of summoning each participant for the collection of data for the first evaluation. Each participant will be given an evaluation questionnaire of sociodemographic, clinical and psychological variables that he/she will have to bring completed for the day of the appointment. Also, each participant will be given four saliva collection bottles, which they will have to collect four times the day before their appointment. The times of collection of these saliva samples will be upon waking up, 30 minutes later, before lunch (between 13:00 and 13:30) and before dinner (between 20:00 and 20:30). The saliva samples will be collected by the program coordinator at the Onkologikoa Foundation and will be coded and managed by the Biobanko. Subsequently, they will be taken to the Psychobiology laboratory of the UPV/EHU for the determination of different biological variables. In addition,

participants will have to undergo a blood draw on the day of the appointment. The blood collection will be performed by a nurse member of the research team of the Onkologikoa Foundation. The blood samples will be coded and managed by the Biobanko. Subsequently, they will be transferred to the Psychobiology laboratory of the UPV/EHU for the determination of different biological variables.

After this first collection of clinical, psychological and biological data, patients will be randomly selected, through a balanced block randomization method, to be part of the experimental group 1 (EG1) or the experimental group (EG2). As this is a crossover design clinical trial, patients in GE1 will start the peer social support program before the start of medical treatment, while patients in GE2 will start the peer social support program after the end of medical treatment.

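### The EG1–EG2 ANOVA does not list the evaluation 1 outcome value as a covariate, which costs precision; secondarily, duration of medical treatment needs defining as planned or realised

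*Combined protocol and SAP*

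**What the plan says.** DATA ANALYSIS fixes one covariate set for everything: "In all the analyses performed, the following variables will be controlled: type and duration of medical treatment and pharmacological treatment". It then names repeated measures analyses for the within-patient effect of the programme and, separately, an ANOVA for differences between EG1 and EG2 (also written GE1 and GE2). The ANOVA has no stated time point, dependent variable or model formula. No group-by-time term is mentioned.

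METHODS gives the order of events:

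- Patients enter "not having started medical treatment", and a further entry condition is "the tumor type and medical treatment coinciding with any of the volunteers".
- Before the first appointment each receives an "evaluation questionnaire of sociodemographic, clinical and psychological variables"; saliva and blood are also taken.
- Allocation follows: "After this first collection of clinical, psychological and biological data, patients will be randomly selected, through a balanced block randomization method".
- Evaluation 2 comes after the programme in EG1. For the other arm: "In GE2, the evaluation of clinical, psychological and biological variables will be carried out four months after the first evaluation".
- The later visits are timed from the end of treatment: "A third evaluation of all participants will be carried out 15 days after receiving the news of the end of the medical treatment", and then "At four months and eight months after the end of medical treatment (chemotherapy or radiotherapy), the fourth and fifth evaluations will be carried out".

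The VARIABLES section lists medical treatment among the clinical variables, but not its duration, planned or realised.

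**The concern.** EG1 versus EG2 is the only randomised contrast in the trial, and it carries the aim of learning when the programme works best. Every outcome is measured before allocation, so its evaluation 1 value is a covariate that costs nothing to collect and cannot be affected by the arm. The list applied to all analyses does not include it. What is at stake is precision, together with protection against a chance difference between arms at the start.

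The list does include duration of medical treatment, undefined. Since nobody has started treatment at entry, a realised duration can only become known after randomisation. EG1 support begins before treatment and runs alongside it, while EG2 has none until treatment is over. If realised duration is meant, the randomised comparison would condition on something that follows allocation. At evaluation 2, about four months in, that duration is also incomplete for anyone still on treatment.

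**Working it through.** **Inputs.** The 120 patients come from METHODS, which gives no alpha, power, effect size, SD or dropout for them, so there is no calculation of the plan's own to reproduce. Assumptions, none from the documents: 60 per arm (read from balanced blocks), no losses, effect 0.4 SD, two-sided 5%, and ρ for the correlation between the evaluation 1 and follow-up scores.

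**1. Gain from the evaluation 1 score.** Adjustment multiplies the residual variance by 1 − ρ².

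SE = √[(2/60)(1 − ρ²)]; power = Φ(0.4/SE − 1.96); effect detectable with 80% power = (1.96 + 0.842) × SE.

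| ρ | 1 − ρ² | SE | Power | Detectable effect (SD) |
|---|---|---|---|---|
| none | 1.00 | 0.183 | 59.1% | 0.51 |
| 0.3 | 0.91 | 0.174 | 63.2% | 0.49 |
| 0.5 | 0.75 | 0.158 | 71.6% | 0.44 |
| 0.7 | 0.51 | 0.130 | 86.6% | 0.37 |

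With the noncentral t, the three adjusted powers are 62.5%, 70.9% and 86.1%.

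**2. Chance imbalance.** Under randomisation the difference in evaluation 1 means has standard error √(2/60) = 0.183 SD. An imbalance of that size moves the unadjusted estimate by ρ × 0.183, which is 0.05, 0.09 and 0.13 SD at ρ = 0.3, 0.5 and 0.7. Over repeated randomisations this averages to zero, so it is noise and not bias.

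**3. Adding the score versus swapping it for duration.** Let r be the assumed correlation of duration with the outcome, with duration independent of the evaluation 1 score and of allocation. The variance factor with both covariates is 1 − ρ² − r².

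- Duration alone, r = 0.3: factor 0.91, power 63.2%.
- Score added, ρ = 0.3: factor 1 − 0.09 − 0.09 = 0.82, power 67.7%.
- Score added, ρ = 0.5: factor 1 − 0.25 − 0.09 = 0.66, power 76.9%.
- Score in place of duration: no gain at ρ = r = 0.3 (63.2% either way), and a loss at ρ = 0.2, r = 0.4 (60.9% against 66.7%).

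A simulation of 20,000 trials agrees. At r = 0.3, power goes from 0.617 with duration to 0.662 with both (ρ = 0.3), and from 0.619 to 0.752 (ρ = 0.5).

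**4. Realised duration.** Suppose allocation shifts realised duration by δ SD. The adjusted group estimate then differs from the unadjusted one by r × δ, in either direction.

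- δ = 0: no difference.
- δ = 0.1, r = 0.2: 0.02 SD. δ = 0.3, r = 0.4: 0.12 SD.

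Simulation with 2,000,000 patients per scenario and r = 0.3:

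- δ = 0: −0.400 unadjusted and −0.400 adjusted.
- δ = 0.2, duration and outcome sharing a cause: −0.399 unadjusted and −0.459 adjusted, which is bias.
- δ = 0.2, duration lying on the path to the outcome: total effect −0.339, adjusted −0.399, which is a change of estimand.

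The values of δ and r have no source in the documents.

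**The case against.** A reader might infer from the undefined duration that the randomised comparison is biased. The documents do not support that. It requires both that realised duration is meant and that allocation changes it. The first is open: treatment type must be known at entry for matching to a volunteer, so a planned duration may exist too. On the second, no section describes a way in which support sessions would lengthen or shorten chemotherapy or radiotherapy. This is a risk left open, not a bias shown.

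A reader might also infer that the evaluation 1 score is excluded from every analysis. The text shows only that it is not listed. The repeated measures analyses may carry it as a time level, and the ANOVA could be run on change scores. What stands is that the repeated measures analyses are described as within-patient and no group-by-time term is given, so the stated between-group model does not contain the score.

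The strongest objection concerns dropping realised duration altogether. Evaluations 3 to 5 are timed from the end of treatment, so realised duration largely sets the time since randomisation and, in EG1, since the programme ended. The sponsor may have meant to control it for that reason. In addition, no section says that a planned duration is recorded, so a model confined to planned values might lose duration entirely. This stands: the score should be added, not swapped in, and the treatment of duration at the later visits is a trade-off to be shown openly.

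The pharmacological covariate also lacks a time point. Evaluation 1, where the clinical questionnaire is given, is the natural reading. This is a wording clarification only.

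**Conclusion.** The point holds as a low-cost improvement in precision. The stated EG1–EG2 model does not include the evaluation 1 value of the outcome. Adding it would raise power from 59% to between 63% and 87% for ρ from 0.3 to 0.7 against no covariates, or from 63% to 68% (ρ = 0.3) or 77% (ρ = 0.5) if a duration covariate with r = 0.3 is already in the model. All of this rests on the assumed 60 per arm and 0.4 SD effect. Correlations will differ between questionnaires, cytokines and cortisol, and at low ρ the gain is small. The 0.4 SD illustration also does not separate visits: by evaluation 4, EG2 will itself have been receiving the programme, so the contrast there is early versus late support.

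The duration point is secondary and conditional. Its size is zero if allocation leaves duration unchanged, and 0.02 to 0.12 SD for the assumed shifts and correlations. Confidence is medium.

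**What to change.** Add to DATA ANALYSIS wording such as:

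*EG1–EG2 comparisons use ANCOVA, or a mixed model over evaluations with a group-by-time term, that adds the evaluation 1 value of each outcome to the listed covariates. Duration of medical treatment means planned duration where this is recorded before randomisation. Realised duration is not used in the evaluation 2 comparison. At evaluations 3 to 5 the comparison is reported with and without realised duration. Pharmacological treatment is taken as recorded at evaluation 1.*

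VARIABLES should say whether planned duration is recorded and when. Duration can remain in the correlation and prediction analyses, which are not randomised contrasts.

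The baseline term costs one degree of freedom per outcome and needs no new data. Leaving realised duration out at evaluation 2 may lose some precision if it is prognostic and unaffected by allocation: under the same assumptions, 72% against 77% power at ρ = 0.5, r = 0.3, and 63% against 68% at ρ = 0.3, r = 0.3. Those figures treat duration as fully known; at evaluation 2 it is incomplete for patients still on treatment. Planned duration, if recorded, would limit the loss. Reporting evaluations 3 to 5 both ways costs one extra analysis per outcome and visit.

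### Age, tumour stage and tumour type are collected before randomisation but left off the control list: a confounding risk in the biomarker-questionnaire correlations, and only a small precision cost in the EG1-EG2 contrast

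*Combined protocol and SAP*

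**What the plan says.** DATA ANALYSIS gives one control list for all analyses: "the following variables will be controlled: type and duration of medical treatment and pharmacological treatment". It then plans four kinds of analysis:

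- Within-person: "Repeated measures analyses will be performed to study the effect of the intrasubject support program".
- Between groups: for "differences between experimental groups 1 and 2, analysis of variance (ANOVA) will be carried out".
- Association: "Pearson's correlation coefficient will be used to analyze the relationships between the different physiological and psychological variables".
- General linear models for the predictors of benefit. The candidate predictors are not named.

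VARIABLES shows that the omitted covariates are held. The list opens with age ("The sociodemographic and clinical variables to be collected are: age, marital status, employment status") and ends with "tumor type, stage and medical treatment".

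METHODS fixes the timing: "After this first collection of clinical, psychological and biological data, patients will be randomly selected, through a balanced block randomization method". It names no stratification factor. On the sample it says: "The patients in this study will be 120 patients with various types of cancer". Relapse is excluded, and tumour type and treatment must match those of a volunteer. No eligibility criterion restricts stage.

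**The concern.** Age, stage and tumour type are known at evaluation 1, so allocation cannot affect them. The plan controls for features of treatment and leaves these three out. Treatment type carries some information about stage and tumour type, but only part of it.

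The consequence differs by analysis. The AIMS section itself links the measured biological systems both to anxious-depressive symptoms and to the progression of cancer. A cytokine and a distress score could therefore correlate because both follow disease extent, with no direct link between them. Age could act in the same way, for example through the sex hormones. Randomisation gives no protection here, because no randomised groups are being compared. In the EG1-EG2 contrast, which is randomised, only precision and chance imbalance are at stake.

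**Working it through.** The plan gives N = 120 but no alpha, power, effect size or SD, so it has no calculation to reproduce. The figures below are illustrations. Assumed: two-sided alpha of 0.05; 60 patients per group (the plan says balanced blocks but gives no ratio); no dropout; and the covariate strengths shown, taken as what remains after the planned control for treatment.

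**1. Correlations.** If a covariate correlates *a* with both measures and nothing else links them, the induced correlation is r = a². Its chance of reaching p < 0.05 follows from Fisher's z: m = atanh(r) × √(120 − 3), and P = 1 − Φ(1.96 − m) + Φ(−1.96 − m).

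| a (assumed) | r = a² | m | P(significant) |
|---|---|---|---|
| 0.2 | 0.04 | 0.43 | 7% |
| 0.3 | 0.09 | 0.98 | 16% |
| 0.4 | 0.16 | 1.75 | 42% |

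The nominal rate is 5%.

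**2. Group contrast: is there bias?** An unadjusted two-group comparison was simulated with a prognostic covariate left out and no true effect (20,000 runs, 60 per group). With the covariate explaining 10% of outcome variance, the mean difference was −0.0005 SD and the type I error 5.2%. At 30% they were 0.0026 SD and 4.9%. There is no systematic bias.

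**3. Group contrast: chance imbalance.** The SD of a standardised baseline difference is √(2/60) = 0.183, so P(|difference| > 0.25) = 17%. An imbalance of 0.25 shifts the contrast by 0.25 × √R²: 0.06 SD at R² = 5% and 0.10 SD at R² = 15%. The difference detectable with 80% power is (1.96 + 0.84) × 0.183 = 0.51 SD.

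**4. Group contrast: precision.** Adjustment for k covariates multiplies the variance of the contrast by (1 − R²) on average, but also by (N − 3)/(N − 3 − k) for normal covariates. That factor is 117/114 = 1.026 for k = 3 and 117/112 = 1.045 for k = 5. The interval ratio (adjusted to unadjusted) is about √[(1 − R²) × 117/(117 − k)], with a very small further change in the t quantile.

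| R² (assumed) | k | Interval ratio | Narrower by | Unadjusted wider by |
|---|---|---|---|---|
| 5% | 3 | 0.988 | 1.2% | 1.2% |
| 5% | 5 | 0.997 | 0.3% | 0.3% |
| 15% | 3 | 0.934 | 6.6% | 7.0% |
| 15% | 5 | 0.943 | 5.7% | 6.1% |

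Without the degrees-of-freedom cost the narrowing would read 1 − √(1 − R²) = 2.5% to 7.8%. At the low end most of that disappears.

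**The case against.** A reader might infer from the omission that disease severity biases the comparison of EG1 with EG2. The documents do not support that. Allocation is by balanced block randomisation after evaluation 1, and the simulation above shows no bias and a correct error rate. Chance imbalance is already allowed for in the test's error rate. Age is also not a measure of severity.

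Other points on that side also stand, at least in part:

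- **Overlap.** Treatment type is controlled, and volunteer matching ties tumour type to treatment. Only what the omitted variables add beyond treatment type counts, and that may be small.
- **Predictor models.** They are to examine each of the variables and may already contain age, stage and tumour type. It cannot be said that the variables are missing from them, only that the plan does not name the set.
- **Repeated measures.** Stable baseline characteristics largely cancel from the main effect in within-person change, though they can still modify the time course.
- **Peripheral analyses.** The stated aims are intervention effects and timing. The biomarker-questionnaire correlations appear only under DATA ANALYSIS.
- **A different problem in the same sentence.** Treatment duration is known only after randomisation, so adjusting the group contrast for it can itself cause bias. Adding baseline covariates does not cure that, and it needs its own decision.

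The objection does not remove the confounding risk in the correlations.

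**Conclusion.** The point holds in limited form and is minor. The control list omits three variables that are already collected before randomisation, and no stratification is stated.

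In the Pearson correlations this is a real confounding risk. The induced r is about 0.04 to 0.16, with false-positive rates of about 7% to 42%, if the covariate correlates 0.2 to 0.4 with both measures net of treatment type. Those correlations are assumed; the documents give no values.

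In the EG1-EG2 contrast there is uncorrected chance imbalance and a precision loss of roughly 0% to 7% in interval width, for an assumed R² of 5% to 15%. A claim of bias in that contrast, or of proven omission from the predictor models, would go beyond the text.

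**What to change.** Change the wording of DATA ANALYSIS as follows:

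1. For the biomarker-questionnaire associations, use partial correlations or regression adjusted for evaluation-1 age and stage (two levels, with the split defined in advance). Add a coarse tumour-type grouping where treatment type does not already determine it. A plain Pearson coefficient controls for nothing, so the method of adjustment has to be stated in any case.
2. Name the variables in the predictor models and state that age, stage and tumour type are among them.
3. In the EG1-EG2 comparison, add evaluation-1 age and stage as precision covariates, and describe them as such and not as a correction for bias.

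No new data are needed. The cost is about 3 to 5 degrees of freedom out of 120 patients, and the need to fix the stage split and tumour grouping before the data are seen. If these variables add little beyond treatment type, the gain will be close to nil.
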